### Unscheduled visits due to self-measured increase of IOP

Analysis of number of unscheduled visits due to self-measured increased IOP will be performed analogue to the analysis for incidence rates of AEs (see Section 7.7). The rate of unscheduled visits due to self-measured increase of IOP per 10 patient years and accompanying exact 95% confidence intervals will be calculated, assuming that the number of such events is Poisson distributed.

## 7.7 Evaluation of Primary Safety Variables

All recorded AEs will be coded using the MedDRA version in effect at the time the database is closed. Events that undergo worsening or improvement (i.e., changes in severity) prior to resolution will be evaluated as single events using the worst severity reported during its course. Only eye-related AEs will be included in the analysis while remaining AEs will be listed only. The categorization of AEs into eye-related / not eye-related will be done by a medical expert before start of the statistical analysis. In addition, it will be determined whether the eye-related AE occurred in the study eye or fellow eye under consideration of all information recorded for the AE in the eCRF. If an eye-related AE can not unequivocally be assigned to an eye, it will be assigned to the study eye.

Incidence will be calculated for eye-related AEs, medical device related AEs and, in case there are more than five (5) events, also for medical device related SAEs on the system organ class level and on the preferred term level, in total (i.e., number and percentage of subjects with any/respective AE and number of any/respective AE) and by worst severity and seriousness (i.e., number and

percentage of subjects with any/respective AE). In case of the analysis of all eye-related AEs, the analysis will be done by eye (study eye / fellow eye) and overall.

In order to evaluate the long-term safety, the incidence rate of medical device related adverse events per 10 patient years and accompanying exact 95% confidence intervals will be calculated, assuming that the number of such adverse events is Poisson distributed. The incidence rate per 10 patient years will be calculated as 10 times the number of medical device related AEs divided by the number of patient years. Patient years will be defined as the sum of the individual on-study times from first visit (V01) until date of study completion/last attended study visit / last medical device related adverse event (whichever is later).

This calculation will also be done for AEs of special interest and medical device related SAEs. The definition of AEs of special interest will be done by a medical expert prior to start of the statistical analysis.

Listings for eye-related AEs leading to discontinuation, serious AEs, and deaths will also be provided.

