7.1.4 Primary Outcome Variables

Safety:

- Incidence of medical-device related adverse events

 Implantata Ophthalmic Products GmbH	Clinical Investigation Plan ARGOS-03	Revision C Page 43 of 67
--------------------------------------------------------------------------------------------------------------------------	-------------------------------------------------------	---------------------------------

- Incidence of medical-device related serious adverse event.
 - o An AE is considered to be device-related if there is at least a possible relationship to the medical device according to the rating of the investigator
 - o An AE is considered to be serious if it meets any of the criteria defined in Section 9.1.1.2

The analysis will be split by nature, severity and seriousness of medical device related adverse and serious adverse events.

Performance:

- Limits of agreement between IOP measurements made using GAT and the ARGOS-IO system at each study visit.
- Limits of agreement between IOP measurements made using DCT and the ARGOS-IO system at each study visit.
- Incidence of observed device malfunctions and nature of device malfunction (e.g. difference of more than 5 mmHg between ARGOS-IO and GAT, readout error of the Mesograph because of measurements outside -2 and +70mmHG).

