7.2.3 Analysis of Primary Safety Outcome Variables

All recorded AEs will be coded using the Medical Dictionary for Regulatory Activities (MedDRA) in effect at the time the database is closed. Only eye-related AEs will be included in the analysis.

Incidence will be calculated for eye-related AEs, medical-device related AEs and, in case there are more than 5 events, also for medical-device related SAEs on the system organ class level and on the preferred term level.

In addition to incidences in total, incidences will be given by severity and seriousness.

 Implantdata Ophthalmic Products GmbH	Clinical Investigation Plan ARGOS-03	Revision C Page 45 of 67
---------------------------------------------------------------------------------------------------------------------------	-------------------------------------------------------	---------------------------------

In order to evaluate the long-term safety, the incidence rate of medical-device related adverse events per 10 patient years and accompanying exact 95% confidence intervals will be calculated for the safety population, assuming that the number of such adverse events is Poisson distributed. The incidence rate per 10 patient years will be calculated as the number of medical-device related AEs divided by patient years covered in the study multiplied by 10 patient years. Patient years covered in the study will be defined as the sum of the individual on-study times from Baseline Visit (V01) until date of study completion.

This calculation will be also done for AEs of special interest and medical-device related SAEs.

Since reliability of the incidence rates strongly depends on the number of patient years covered by the single patients in the study, the on study time of each patient will be analyzed additionally.

Listings for eye-related AEs leading to discontinuation, serious AEs, and deaths will also be provided.

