### 6.5 Primary Safety Variables

The following safety variables are planned to be evaluated:

- Incidences of medical device related adverse events
- Incidences of medical device related serious adverse events

- An AE is considered to be device related if there is at least a possible relationship to the medical device according to the rating of the investigator
- An AE is considered to be serious if it meets any of the criteria defined in Section 9.1.1.2 of the CIP

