#### 8.3 Safety data

- 8.3.1 Adverse Events (AEs) and device related adverse events (ADEs)
  - 8.3.1.1 Overall summary of AEs
  - 8.3.1.2 Overall summary of ADEs
  - 8.3.1.3 Subjects with eye-related AEs and number of eye-related AEs by SOC and PT
  - 8.3.1.4 Subjects with eye-related ADEs and number of eye-related ADEs by SOC and PT
  - 8.3.1.5 Subjects with eye-related AEs by worst severity, SOC and PT
  - 8.3.1.6 Subjects with eye-related ADEs by worst severity, SOC and PT
  - 8.3.1.7 Subjects with eye-related AEs by seriousness, SOC and PT

- 8.3.1.8 Subjects with eye-related ADEs by seriousness, SOC and PT
- 8.3.1.9 Eye related ADEs per 10 patient years
- 8.3.2 Deaths and other serious / significant adverse events
- 8.3.2.1 Serious AEs, listing of subjects
- 8.3.2.2 Deaths, listing of all serious AEs of subjects who died
- 8.3.2.3 AEs leading to discontinuation, listing of subjects

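### The primary safety variables cover all device-related AEs and SAEs, but the analysis admits only eye-related events, so the defined variable is not quite what is estimated

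*SAP*

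**What the plan says.** **Definition.** Protocol 7.1.4 takes device-related AEs and SAEs as the primary safety variables and sets the rule for relatedness: "An AE is considered to be device-related if there is at least a possible relationship to the medical device", as rated by the investigator. SAP 6.5 repeats the rule and names the first variable as "Incidences of medical device related adverse events". Neither place limits the variable to the eye. SAP 2.4.2 makes safety a co-primary objective.

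**Analysis.** Protocol 7.2.3 states "Only eye-related AEs will be included in the analysis". SAP 7.7 carries this forward: "Only eye-related AEs will be included in the analysis while remaining AEs will be listed only". Who decides is also fixed: "The categorization of AEs into eye-related / not eye-related will be done by a medical expert before start of the statistical analysis". No criterion for eye-related is given.

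**Rate.** Later in SAP 7.7 the rate is "calculated as 10 times the number of medical device related AEs divided by the number of patient years". Person-time may run to the "last medical device related adverse event (whichever is later"). Neither the formula nor the person-time rule repeats the eye limit.

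**Planned tables.** In the SAP appendix, tables 8.3.1.4, 8.3.1.6, 8.3.1.8 and 8.3.1.9 are titled for eye-related device effects. The last of these is the rate table itself: "Eye related ADEs per 10 patient years". Table 8.3.1.2, the overall summary of device effects, has no eye limit in its title. The appendix adds that the choice and naming of tables are not binding and may be adapted to the analyses described in the text.

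**Changes.** SAP Section 8 lists one change to the planned analysis, which concerns the IOP measurement series. It says nothing about the safety variables.

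**The concern.** The defined variable and the analysed set are different sets of events. An event that the investigator rates as possibly device-related meets the primary definition wherever it occurs. If the expert then classes it as not eye-related, it drops out of the co-primary result and appears only in a listing. Neither document explains why device-related harm outside the eye should be treated this way.

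Such an event is possible. The protocol synopsis counts the antenna patch among the accessories of the medical device, and protocol 4.1 describes it as an adhesive skin patch worn around the eye for more than a day. A skin reaction to it could well be rated device-related. With no written criterion, the expert could class it either way.

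At stake is whether the reported incidence and rate describe what the plan says they describe. The exclusion works in one direction only, towards a more favourable device-related rate.

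**Working it through.** The documents give no event count or expected rate, so there is no plan figure to reproduce. The check is a comparison of text, followed by the effect of one excluded event.

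**Step 1. Which events count.**

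| Place | Events covered | Eye limit |
|---|---|---|
| Protocol 7.1.4, SAP 6.5 (definition) | AEs and SAEs at least possibly device-related | none |
| Protocol 7.2.3, SAP 7.7 opening paragraph (analysis) | AEs classed as eye-related | yes |
| SAP 7.7 rate formula and person-time rule | device-related AEs | not repeated |
| SAP tables 8.3.1.4, .6, .8, .9 | device effects classed as eye-related | yes |

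The opening restriction in SAP 7.7 is general and comes before every calculation in that section. The tables apply it. The natural reading is therefore that the filter governs the numerator, and a device-related event outside the eye is not counted.

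**Step 2. Numerator effect per excluded event.** Inputs: at most 26 subjects (5 + 21; protocol 7.2.7, SAP 2.9); last visit at day 1080; rate = 10 × events / patient-years (SAP 7.7).

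- Patient-years: 26 × 1080 / 365.25 = 76.88.
- Change in rate per event: 10 / 76.88 = 0.130 per 10 patient-years.
- Change in subject incidence if the event was that subject's only device-related AE: 1/26 = 3.8 percentage points.

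No minimum sample size is set, so smaller numbers are shown as assumptions, each fully followed:

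| Subjects | Patient-years | Change in rate per excluded event |
|---|---|---|
| 26 | 76.88 | 0.130 |
| 20 | 59.14 | 0.169 |
| 15 | 44.35 | 0.225 |
| 10 | 29.57 | 0.338 |

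Drop-outs contribute their time on study. If 26 enrol, 10 complete and 16 leave at day 540 (assumption), patient-years are (10 × 1080 + 16 × 540) / 365.25 = 53.22 and the change is 0.188.

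**Step 3. Illustration with exact Poisson limits.** Event counts are assumed, at 76.88 patient-years. Two eye-related device effects give 0.26 per 10 patient-years (95% CI 0.03 to 0.94). Adding one that is not eye-related gives 0.39 (0.08 to 1.14).

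**Step 4. Denominator effect.** The person-time rule counts any device-related AE, so an event excluded from the numerator could still lengthen follow-up. Suppose 25 subjects reach day 1080 and one last attends at day 900: (25 × 1080 + 900) / 365.25 = 76.39 patient-years. An excluded event in that subject at day 930 gives 76.47, which lowers the rate by 0.11% in relative terms. At day 1080 it gives 76.88, a fall of 0.64%. This is negligible.

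**The case against.** The strongest reply is that the plan is consistent where it matters. Protocol 7.2.3 sets the eye-related rule, SAP 7.7 repeats it before any calculation, and four tables apply it, including the rate table. Most of this stands. A reader might infer from the unrestricted rate formula, and from device-related and eye-related AEs being named side by side, that SAP 7.7 offers two competing numerators. The documents do not support that. The same sentence also names device-related SAEs separately, although they are a subset of device-related AEs, so separate naming does not put an item outside the filter. The note that table titles are not binding only makes the tables follow the text, and the text contains the filter. The wording of the formula and the person-time rule is loose, but that is secondary.

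Several replies limit the importance of the point, and they also stand. The safety objective is worded for the pressure sensor, which sits inside the eye, and the AEs of special interest in protocol 5.3 are essentially ocular. Use of the patch is optional and at most quarterly, and the component list that opens protocol 4.1 omits it. Excluded events are still listed, may appear in table 8.3.1.2, and if serious fall under the SAE listing 8.3.2.1, whose title has no eye limit. A reader might infer that harm would be concealed; it would not.

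It can also be said that adding the eye limit to the definitions would cure the mismatch equally well. It would make the documents agree. But protocol 6.4.3.1 attaches the ophthalmic limit to adverse events in general and not to device effects, and protocol 6.4.4.5 and 9.1.2 call for all device effects to be recorded. Narrowing the definition would remove recorded device-related harm from a co-primary result.

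None of these replies removes the mismatch between the definition and the analysed set.

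**Conclusion.** The point holds as a mismatch between the defined primary safety variables and the set analysed, present in both the protocol and the SAP and acknowledged in neither. With the filter read as governing, and with the person-time rule as written, the reported device-related rate equals the rate of the defined variable or lies below it.

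The size depends on how many device-related events are classed as not eye-related. The documents give no such number, and it may be zero. Each one costs 0.13 per 10 patient-years at full enrolment and follow-up, and more if patient-years are fewer. The study is exploratory, with no hypothesis, test or success threshold resting on the rate, and in the illustration the intervals overlap almost entirely. The severity is minor: worth correcting because it concerns a co-primary result and the correction is cheap.

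**What to change.** In SAP 7.7, state that the incidence and Poisson rate of device-related AEs and device-related SAEs use every AE rated at least possibly device-related, whatever the body site, and show the eye-related ones as a subset. Keep the eye filter only for AEs not rated device-related. The numerator and the person-time rule then refer to the same events. Align the titles of tables 8.3.1.4, 8.3.1.6, 8.3.1.8 and 8.3.1.9, and record and justify the departure from protocol 7.2.3 in SAP Section 8.

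The cost is a few sentences, four titles and one entry. Under SAP 2.11 the change can be documented in the SAP if decided before database close. After close it must be justified in the final report and identified as data-driven or not. Changing protocol 7.2.3 itself may need a formal amendment and ethics committee approval (protocol 10.3); the SAP Section 8 route documents the change without one.

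No new data should be needed, since protocol 6.4.4.5 and 9.1.2 call for all device effects to be recorded. One check is advisable: the visit schedule's row label can be read as limiting collection to eye-related events, so data management should confirm that device effects outside the eye were captured. The one downside for the sponsor is that the reported rate may become slightly less favourable.

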## 7.8 Evaluation of Other Variables

### Visual acuity

Summary statistics for raw values and change over time will be provided for best corrected visual acuity (BCVA). Results will be presented by eye and visit.

Additionally, summary statistics for raw values and change over time will be provided for subjective and objective refraction (spherical and cylindrical component, axis) and for visual field deviation. Results will be presented by eye and visit.

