## 7. Statistical Analysis Methods

### 7.1 Descriptive Statistics

The default summary statistics for quantitative variables will be the number of non-missing observations (n), number of missing observations (miss), arithmetic mean, standard deviation (SD), lower quartile (Q1), upper quartile (Q3), minimum (min), median, and maximum (max) for those patients with data available.

For categorical variables, the number (n) and percentage (%) of patients per category will be the default summary presentation, and, if applicable, the number of missing values is provided in a “Missing” category. For the number of missing values, only patients that attended the respective visit will be counted. Percentages will be calculated using a denominator of all patients with non-missing data. If necessary, the denominator will be specified in a footnote to the tables for clarification.

All tables including calculation of change over time (Visit 01 vs Visit 02 – Visit 07) will also include summary tabulations for the raw values of the respective variable analysed.

In case of analyses per eye, results will be grouped by study eye / fellow eye instead of right eye / left eye.

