## 7.3 Data Derivation

### 7.3.1 Change Over Time

Whenever the change over time is analyzed, the result at the start of the time period of interest (usually Visit 01) is subtracted from the result at the end of the time period of interest (usually Visit 02 – Visit 07)

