#### 7.3.5 Derivation of Other Variables

Manifest refraction spherical equivalents will be derived from their cylindrical and spherical components according to the following formula:

$$\text{MRSE} = \text{Spherical component [D]} + 0.5 \text{ cylindrical component [D]}$$

Cylindrical component (CYL) of manifest refraction can be indicated as plus CYL diopter using plus cylinder notation or alternatively, as minus CYL value at axis rotated through 90° using minus cylinder notation. Both notations are equivalent, but including both notations in the same analysis leads to incorrect estimate of mean of spherical (SPH) and of CYL variables. The conversion from one notation to the other influences also the spherical component of spherocylindrical correction. Therefore, a conversion of cylindrical component, sphere and axis are required in case data was recorded in minus notation. To convert minus into plus notation, the following formula is used:

$$\text{SPH}' = \text{SPH} + \text{CYL}$$

$$\text{CYL}' = -\text{CYL}$$

$$\text{Axis}' = \text{Axis} + 90^\circ$$

In case the resulting axis value (Axis') is greater or equal to 180°, 180° will be subtracted to determine the final axis value. No changes will be made to positive notations.

Best corrected visual acuity (BCVA) will be provided in Snellen. For preparation of summary statistics, these will be converted to logMAR according to Holladaya as follows:

- 1) Convert Snellen visual acuity to equivalent decimal acuity (e.g. 20/40 = 0.50)
- 2) LogMAR = -log(Decimal acuity)

---

a Holladay, J.T. (1997): Proper Method for Calculating Average Visual Acuity. J Refract Surg 13:388-91.

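### The SAP prescribes linear means and plain differences for cylinder axis, which has a 180° period, so axis summaries are not interpretable when axes lie near 0°/180°

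*SAP*

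**What the plan says.** Four parts of the SAP bear on this.

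- **Section 7.8, Visual acuity.** It specifies summary statistics, both raw and as change over time, for "subjective and objective refraction (spherical and cylindrical component, axis"), by eye and visit. Section 6.6 also names axis among the additional variables evaluated at each visit.
- **Section 7.1.** The default set for quantitative variables includes "arithmetic mean, standard deviation (SD), lower quartile (Q1), upper quartile (Q3), minimum (min), median, and maximum (max"). All of these treat the scale as linear.
- **Section 7.3.1.** For change, the starting value "is subtracted from the result at the end of the time period of interest". There is no special rule for angles.
- **Section 7.3.5.** Refractions recorded in minus-cylinder notation are converted to plus notation by adding 90° to the axis. If the result is 180° or more, "180° will be subtracted to determine the final axis value". The reason given for harmonising is that mixed notation "leads to incorrect estimate of mean of spherical (SPH) and of CYL variables". Nothing is said about averaging axis.

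No section restricts axis to listings, defines a circular mean or reduces axis differences modulo 180°.

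**The concern.** A cylinder axis is an orientation: 0° and 180° are the same axis, and 5° and 175° are 10° apart. The SAP recognises this when it converts notation but not when it summarises. A programmer following sections 7.8, 7.1 and 7.3.1 has one available reading, which is to average and subtract axis as if it were a length.

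At stake is whether the axis rows can be read at all. Eyes with stable astigmatism could appear to rotate by about 170°, and a visit mean could be perpendicular to the axis of every eye in the group. With at most 26 patients (SAP section 2.9), one or two such values are enough to distort a row.

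**Working it through.** The plan states no figure on this point, so there is none to reproduce. The check applies the SAP's own rules to example axes and compares the results with arithmetic that respects the 180° period.

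**1. Mean of 5° and 175°.**
- SAP rule (7.1): (5 + 175)/2 = 90°. The median is also 90°.
- Axial mean: double the angles to 10° and 350°. The mean cosine is 0.985 and the mean sine is 0, so the doubled direction is 0° and the axis is 0°/180°.
- The SAP result is perpendicular to the correct one.

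**2. Change from 175° to 5°.**
- SAP rule (7.3.1): 5 - 175 = -170°.
- Signed difference within ±90°: ((-170 + 90) mod 180) - 90 = 100 - 90 = +10°.
- In reverse, from 5° to 175°, the SAP gives +170° and the correct value is -10°.

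**3. Does the notation conversion cure it?** Take minus-cylinder axes of 85° and 95°, whose mean of 90° is correct in that notation. Under 7.3.5 they become 175° and 95 + 90 - 180 = 5°. Their arithmetic mean is still 90°, but the correct plus-cylinder axis is now 0°/180°. Here the conversion creates the wrap.

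**4. Weight of one wrapped value.** Recording -170° instead of +10° is an error of 180°. In a table of 26 eyes it moves the mean change by 180/26 = 6.9°.

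**5. Dependence on where the axes lie.** The documents give neither an axis distribution nor a visit-to-visit variability, so the following inputs are assumptions: 26 eyes, axes normally spread about a centre with SD 10° or 20°, true change with SD 7°, 4,000 runs.

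| Centre | Spread SD | Mean absolute error of mean axis | Changes wrapped | SD of tabulated change (true 7°) |
|---|---|---|---|---|
| 0°/180° | 10° | 77.1° | 19.5% | 74.4° |
| 0°/180° | 20° | 78.3° | 10.7% | 53.5° |
| 15° | 10° | 12.1° | 8.2% | 45.2° |
| 15° | 20° | 40.6° | 8.3% | 45.9° |
| 30° | 10° | 1.7° | 0.6% | 10.9° |
| 30° | 20° | 12.2° | 3.8% | 28.6° |
| 45° | 10° | 1.6° | 0.0% | 7.0° |
| 45° | 20° | 3.9° | 0.9% | 13.1° |
| 90° | 10° | 1.5° | 0.0% | 7.0° |
| 90° | 20° | 3.1° | 0.0% | 6.9° |

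The residual error at 90° is ordinary sampling error. For SD 10° the expected absolute error of a mean of 26 is about 0.80 × 10/√26 = 1.6°, and for SD 20° it is 3.1°. With axes spread uniformly and a true change SD of 5° (also assumed), about 2.2% of changes wrap and the tabulated SD of change is about 26°.

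**6. What is untouched.** Sphere and cylinder are linear quantities and are put in one notation before averaging. BCVA is summarised as logMAR. The spherical equivalent is sphere plus half the cylinder and does not use axis.

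**The case against.** A reader might infer that all the refraction results are meaningless, or that any induced astigmatism would be hidden or invented. The documents do not support either. Section 7.8 also summarises cylinder, raw and as change, after conversion to plus notation, so a growing astigmatism would show there whatever happens to axis. Only orientation is distorted. Implantation took place in the earlier studies (SAP section 2.2), so change from Visit 01 does not measure surgically induced astigmatism in any case.

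The other side has further fair points:

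- Section 7.8 says only summary statistics. The arithmetic mean comes from a default in 7.1, and the appendix allows tables to be adapted. That leaves room to do better, but no alternative for axis is specified, so the default is what would be programmed.
- The largest simulated errors need axes that straddle 0°/180°. A cluster lying wholly on one side, such as 165° to 179°, averages normally. This stands and limits the claim about size.
- Axis matters little here. It is an additional variable in a descriptive study without a hypothesis. Protocol section 7.1.6 lists BCVA but not refraction among the additional outcomes, and astigmatism is not among the events of special interest in protocol section 5.3. This also stands and sets the severity.

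None of this removes the defect. The rule as written gives a wrong answer for ordinary data values.

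**Conclusion.** Wrong as written, minor. Sections 7.8, 7.1 and 7.3.1 together prescribe linear statistics for a quantity that 7.3.5 handles with a 180° period. That axes of 5° and 175° average to 90°, and that a +10° rotation is tabulated as -170°, follows from the SAP's rules without any assumption. How often this would happen, and how far the tables would be off, depends on an axis distribution that the documents do not give. Under the assumed inputs the error ranges from none beyond sampling noise, for axes near 90°, to a mean axis about 77° to 78° wrong, for axes near 0°/180°. The finding is confined to the axis rows. No primary or secondary result depends on them.

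**What to change.** In SAP section 7.8, remove axis from the summary statistics and change-over-time tables and state that it is listed only. Mark it the same way in section 6.6, and name it in the refraction or visual acuity listing. This is sufficient.

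Optionally, if astigmatism orientation is to be summarised, derive

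- J0 = -(C/2) cos(2 × axis)
- J45 = -(C/2) sin(2 × axis)

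where C is the cylinder, and report both, raw and as change from Visit 01, by eye and visit. They take the same value in plus and minus notation and average correctly. For two eyes with equal C at 5° and 175°, mean J0 is -0.49C and mean J45 is 0, which is the 0°/180° orientation. The spherical equivalent could be reported beside them. Section 7.3.5 already provides for it ("Manifest refraction spherical equivalents will be derived from their cylindrical and spherical components"), but neither 6.6 nor the visual acuity part of 7.8 names it for analysis.

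The cost is a few words in the SAP and, for the option, two derived variables. No new data are needed. If the database is already closed, the change should be recorded in the clinical investigation report, as section 2.11 requires.
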